5 TRIAL SETTING

This will be a single-centre open-label study, conducted by the Cardiovascular Research Unit, University of Sheffield within the Clinical Research Facility at the Northern General Hospital, Sheffield.

Participants will be healthy volunteers, recruited primarily from local higher education establishments, but also staff from local healthcare institutions.

6 PARTICIPANT ELIGIBILITY CRITERIA

6.1 Inclusion criteria

To participate in this trial, subjects must meet all of the following criteria:

1. Healthy male subjects, or female subjects not of childbearing potential (either surgically sterile or post-menopausal)
2. Age between 18 and 65 years inclusive
3. Non-smokers
4. Body mass index (BMI) between 18 and 28 kg/m² inclusive, with a body weight between 60-100 kg
5. In good health as determined by a medical history, physical examination, vital signs and clinical laboratory test results, including renal and liver function, and full blood count
6. Provision of informed consent before any trial-related activity

6.2 Exclusion criteria

Subjects meeting any of the following criteria will be excluded from participation in the study:

1. Any history of cancer, diabetes or, in the opinion of the investigator, clinically-significant cardiovascular, respiratory, metabolic, renal, hepatic, gastrointestinal, haematological, dermatological, neurological, psychiatric or other major disorders.
2. Any history of either significant multiple drug allergies or known allergy to the study drugs or any medicine chemically related to the study drugs.

3. A clinically-significant illness within the preceding 2 weeks.
4. Any clinically-significant abnormal laboratory test result (full blood count, urea & electrolytes [sodium, potassium, urea and creatinine], liver function tests, clotting screen, urinalysis), at screening (visit 1), in the opinion of the investigator.
5. A supine blood pressure at screening, after resting for 5 minutes, higher than 150/90 mmHg or lower than 105/65 mmHg.
6. A supine heart rate at screening, after resting for 5 minutes, outside the range of 50-100 beats/min.
7. Receipt of any prescribed or over-the-counter systemic or topical medication within the preceding 48 hours.
8. Planned or expected requirement, during the next 3 months (at randomisation, or 3 weeks at the start of period 2), for any non-study systemic or topical prescribed drug, or for systemic or topical over-the-counter NSAID, corticosteroid, antihistamine or any other drug that could affect inflammation, thrombosis or haemostasis in the opinion of the investigator.
9. Receipt of an investigational medicinal product, excluding those for the purposes of this study, within the previous four month period (new chemical entity) or three month period (licensed product) or subjects who have received a vaccine within the previous three weeks.
10. Any donation of blood or plasma in the preceding one month period, excluding for the purposes of this study.
11. A history of alcohol or drug abuse.
12. Mental incapacity or language barriers that preclude adequate understanding.
13. Any other factor that, in the opinion of the investigator, would affect the participant's ability to safely and reliably complete the study, or would affect the scientific validity of the results obtained.

7 TRIAL PROCEDURES

Details of analysis of blood & urine samples

The aim of the analysis of the study samples will be to: (i) show the dose-dependent effects of aspirin on the immune response to endotoxaemia including on inflammatory markers, cytokines, prostanoids, leucocytes, haemostasis and platelet function, and (ii) show whether the addition of ticagrelor modifies these effects.

We will measure inflammatory markers and cytokines that include, but are not limited to, TNF α , IL-6 and CRP.

To determine the detailed effects of aspirin dose modification on circulating prostanoids in the unstimulated and endotoxin-stimulated states, we will measure a panel of eicosanoids and/or their metabolites, including, but not limited to, PGE₂, PG_I₂ and TXB₂ and will additionally assess the effect of ticagrelor on endotoxin-induced responses.

Haemostasis will be assessed by measuring bleeding time pre- and 3 hours post-endotoxin using a method shown to be sensitive to additive effects of antiplatelet agents [33]. The procedure for measuring bleeding time is described in the study-specific SOP relating to this.

Finally, in order to confirm the efficacy of the antiplatelet aspects of the drug regimens being studied, the activity of a broad range of pathways of platelet activation and aggregation will be assessed by light transmittance aggregometry pre-medication, post-medication at peak inflammation and during the resolution phase of inflammation, using arachidonic acid 0.3 and 1 mmol/l, collagen 4 and 16 µg/ml, and ADP 20 µmol/l as agonists.

Study samples will either be measured immediately after collection (eg. light transmittance aggregometry) or stored for assays at a later time (other endpoints).

We will also store acellular samples of serum, plasma, deoxyribonucleic acid (DNA), ribonucleic acid (RNA) and urine within the Cardiovascular Research Unit for future, as yet unplanned, studies. Consent will be sought for this at study enrolment.

7.1 Recruitment

Potential participants will self-identify through established channels of advertisement to local Universities and NHS staff and students, using documents approved for this purpose by the relevant research authorities.

7.1.1 Participant identification

Potential participants will initially self-identify, based on our advertisement, and medically-qualified members of the research team will then determine eligibility.

7.1.2 Screening

Screening will occur at visit 1. The following study procedures will be performed, after obtaining written consent for the study:

- Medical history
- Physical examination
- Collection of demographic data
- Vital signs (pulse, blood pressure and temperature) measured supine after 5 minutes' rest.
- Weight and BMI
- Recording of any concomitant medication
- Safety blood tests: 12.5 ml blood sample for full blood count, urea and electrolytes (sodium, potassium, urea, creatinine), liver function tests and clotting screen

- Urinalysis

7.1.3 Payment

Volunteers who receive at least one endotoxin injection will receive £100 per endotoxin injection (maximum £200) to reimburse them for their time, inconvenience and any discomfort caused. Transportation to and from the Clinical Research Facility will be provided if necessary.

7.2 Consent

Written, informed consent, using the current version of the approved designated form for this study, will be obtained prior to any study procedures being carried out. This will be explained and obtained by a medically-qualified member of the research team, listed on the delegation log. Participants will have the chance to read the ICF/PIS for as long as they need, and will be able to ask any questions, prior to signing. Minors and those judged to be without the mental capacity to provide informed consent will not be enrolled into the study.

Participants will remain free to withdraw at any time from the trial without giving reasons and without prejudicing his/her further treatment and will be provided with a contact point where he/she may obtain further information about the trial. Samples collected up to the point of withdrawal will only be used after withdrawal if the participant consents for this, otherwise they will be destroyed. However, data collected up to that point will be used for analysis, and this will be explicitly stated in the participant information sheet and consent form.

7.2.1 Additional consent provisions for collection and use of participant data and biological specimens in ancillary studies, if applicable

As described above, we will also store acellular samples of serum, plasma, DNA, RNA and urine for future, as yet unplanned, studies. Explicit consent for this will be sought on the consent form at enrolment. Any cellular samples taken will be destroyed before the end of the study.

7.3 The randomisation scheme

Participants will be randomised to one of the following eight treatment sequences, in a 1:1:1:1:1:1:1:1 fashion:

- No IMP for 10-14 days, then \geq 5 week washout period, then no aspirin for 10-14 days, but a loading dose of ticagrelor (180 mg) given one hour before endotoxin injection (sequence 1).
- No aspirin for 10-14 days, but a loading dose of ticagrelor (180 mg) given one hour before endotoxin injection, then \geq 5 week washout period, then no IMP for 10-14 days (sequence 2).
- Aspirin (aspirin lysine) 20 mg BD for 10-14 days, then \geq 5 week washout period, then aspirin (aspirin lysine) 20 mg BD for 10-14 days plus a loading dose of ticagrelor (180 mg) given one hour before endotoxin injection (sequence 3).

- Aspirin (aspirin lysine) 20 mg BD for 10-14 days plus a loading dose of ticagrelor (180 mg) given one hour before endotoxin injection, then \geq 5 week washout period, then aspirin (aspirin lysine) 20 mg BD for 10-14 days (sequence 4).
- Aspirin (aspirin lysine) 75 mg OD for 10-14 days, then \geq 5 week washout period, then aspirin (aspirin lysine) 75 mg OD for 10-14 days plus a loading dose of ticagrelor (180 mg) given one hour before endotoxin injection.
- Aspirin (aspirin lysine) 75 mg OD for 10-14 days plus a loading dose of ticagrelor (180 mg) given one hour before endotoxin injection, then \geq 5 week washout period, then aspirin (aspirin lysine) 75 mg OD for 10-14 days (sequence 6).
- Aspirin (aspirin lysine) 300 mg OD for 10-14 days, then \geq 5 week washout period, then aspirin (aspirin lysine) 300 mg OD for 10-14 days plus a loading dose of ticagrelor (180 mg) given one hour before endotoxin injection (sequence 7).
- Aspirin (aspirin lysine) 300 mg OD for 10-14 days plus a loading dose of ticagrelor (180 mg) given one hour before endotoxin injection, then \geq 5 week washout period, then aspirin (aspirin lysine) 300 mg OD for 10-14 days (sequence 8).

7.3.1 Method of implementing the randomisation/allocation sequence

Randomisation will be handled by an online interactive web-based randomisation service, sealedenvelope.com, using a simple randomisation method.

Participants will be allocated a three-digit number at enrolment (starting at 001) prefixed with 'E01' (e.g. E01001), then if they proceed to randomisation they will be allocated a separate three-digit randomisation number (starting at 001) prefixed with 'R' (e.g. R001).

The system will generate an immediate email to the investigators stating the treatment allocation and this will be printed, one copy being placed in the participant's study file and a further copy sent to the Northern General Hospital Pharmacy with, if appropriate, a study-specific prescription for study medication for period 1. A separate prescription will be issued for period 2 but using the same randomisation document as evidence of the allocation.

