4 TRIAL DESIGN

The trial is a pharmacodynamic study to determine the effect of aspirin dose modification on immune response, compared to control and compared between the presence and absence of potent P2Y₁₂ inhibition with ticagrelor. Healthy volunteers will receive either no aspirin (control group) or one of three doses of aspirin (aspirin lysine) with or without a loading dose of ticagrelor on the last day of the first medication period, as specified in this protocol, for 10-14 days. They will then receive E. coli endotoxin to induce an immune response. Serial measurements of inflammatory markers, cytokines, leucocyte function, prostanoids and platelet function will be taken over 6 hours. Bleeding time will be measured before endotoxin administration and 3 hours after it to assess haemostasis. After a washout period of at least 5 weeks, and not more than 18 weeks, subjects will then crossover to receive the same regimen of aspirin (aspirin lysine) (or no aspirin in the control group) without or with a loading dose of ticagrelor on the last day of the second medication period. The dose-dependent effects of aspirin and the impact of ticagrelor will be compared between the groups.

A total of 72 eligible subjects are planned to be randomised. There will be three regimens of aspirin (aspirin lysine) included in the study, in addition to a control group (no aspirin), each tested with and without a 180 mg loading dose of ticagrelor. Aspirin (aspirin lysine) 75 mg OD represents the current standard regimen in ACS and for primary and secondary prevention of cardiovascular disease. Aspirin (aspirin lysine) 20 mg BD

is a novel regimen hypothesised to provide a better profile of inflammatory and antithrombotic effect than 75 mg OD. Lastly, aspirin 300 mg OD represents a regimen commonly given after coronary artery bypass grafting.

Randomisation will be in a 1:1:1:1:1:1:1 fashion and managed by a commercially available service for this purpose, SealedEnvelope, with whom the sponsor will have a study-specific contract.

E. coli endotoxin will be administered at the end of each treatment period according to the protocol. Subjects will be recruited from the area local to the Northern General Hospital, Sheffield. For example, we will recruit members of staff and students from universities in Sheffield and from Sheffield Teaching Hospitals. Volunteers will be given as much time as they need to consider taking part in the study prior to signing informed consent.

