10 STATISTICS AND DATA ANALYSIS

10.1 Sample size calculation

In our group's previous study of endotoxaemia in 30 participants receiving ticagrelor, clopidogrel or placebo, we saw, after log transformation, a mean 2 hour post-endotoxin plasma TNF- α 1.88 pg/ml with a standard deviation of 0.410 pg/ml.

There is no available raw data and no reliable estimate of the means or standard deviations of the log transformed TNF- α values for any of the three aspirin doses using the same methods. However, a study using a different endotoxin regimen has shown that aspirin 80 mg OD (which is not expected to be significantly different in effect to 75 mg OD) increased peak plasma TNF- α by around 40% compared to those receiving no drug.

We have a clear hypothesis that increasing aspirin dose increases TNF- α , therefore a one-sided test will suffice.

We estimate that clinically-relevant differences in plasma TNF- α at 2 hours post-endotoxin between the dosing regimens might be a 20% increase with 20 mg BD vs. no aspirin, 40% increase with 75 mg OD vs. no aspirin and 60% with 300 mg OD vs. no aspirin, based on the raw data.

These assumptions provide the following sample size estimate:

Test significance level, α	0.050
Number of groups, G	4
Variance of means, $V=S(m_i-m)^2 / G$	0.031
Common standard deviation, s	0.410
Effect size, $D^2 = V/s^2$	0.1828
Power (%)	80
n per group	16

Therefore, when the sample size in each of the 4 groups is 16, a one-way analysis of variance will have 80% power to detect at the 0.050 level a difference in means characterised by a Variance of means, $V=\sum(\mu_i-\mu)^2 / G$ of 0.031, assuming that the common standard deviation is 0.410.

To allow for up to 10% drop-out, the sample size per group will be 18. Drop-outs will not be replaced but it is expected that there will be at least 16 per group after withdrawals.

This sample size calculation was performed by [name] CStat, Senior Consultant, Statistical Services Unit, University of Sheffield, to whom the investigators are grateful.

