10.3.2 Primary outcome analysis

The primary endpoint will be plasma TNF- α at 2 hours following endotoxin administration assessed between aspirin groups (control vs. 20 mg BD vs. 75 mg OD vs. 300 mg OD, without ticagrelor) by one-way ANOVA with treatment as a factor.

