10.6 Interim analysis and criteria for the premature termination of the trial

After discussion between the investigators and the Sponsor, face-to-face participant study visits were halted on 17th March 2020 due to the unprecedented circumstances arising during the coronavirus disease 2019 (Covid-19) pandemic. It was considered by the investigators that the results of the study may have important implications for the management of cardiovascular disease patients who contracted Covid-19 in terms of optimal antiplatelet medication, in view of the morbidity and mortality in Covid-19 associated with dysregulated inflammatory response. It was noted that the recruitment and study activities to date had reached the level that had originally been planned for the study, as per the application funded by the British Heart Foundation. Given the uncertainty regarding restarting the trial, the need to preserve healthcare resources and to limit face-to-face encounters, the investigators and Sponsor decided that an interim analysis should be performed.

Sample size for interim analysis

Data from all participants who have completed visit 3 (first endotoxin day) will be included in the interim analysis. This is expected to include 46 participants who have completed visit 3, 37 of whom have completed the whole study giving a total of 83 endotoxin day visits, anticipated to be split into approximately equal numbers receiving each of the eight study treatment regimens.

Statistical procedure for interim analysis

The primary endpoint of the interim analysis will be plasma TNF- α measured at 2 hours after endotoxin administration assessed between aspirin treatment groups (control vs. 20 mg BD vs. 75 mg OD vs. 300 mg OD, without ticagrelor) using one-way ANOVA.

Should this demonstrate a significant difference between the groups ($p<0.05$), the following pre-specified pairwise comparisons will be performed, in hierarchical fashion:

300 mg OD vs. no aspirin

then, if significant ($p<0.05$)

75 mg OD vs. no aspirin

then, if significant ($p<0.05$)

300 mg OD vs 20 mg BD

then, if significant ($p<0.05$)

75 mg OD vs 20 mg BD

then, if significant ($p<0.05$)

20 mg BD vs no aspirin

Other analyses will be exploratory.

Criteria for premature termination

The trial shall be prematurely terminated if the primary interim analysis demonstrates a statistically significant ($p<0.05$) effect of aspirin dosing on plasma TNF- α two hours after endotoxin injection.

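### Simple randomisation over eight sequences does not secure 18 randomised and at least 16 evaluable per aspirin group, and the primary, interim and paired analyses omit period

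*Protocol*

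**What the plan says.** Protocol section 7.3: "Participants will be randomised to one of the following eight treatment sequences, in a 1:1:1:1:1:1:1:1 fashion". Each aspirin group (none, 20 mg BD, 75 mg OD, 300 mg OD) is made up of two sequences that differ only in whether ticagrelor comes in the first or the second period. Section 7.3.1 says the web service allocates "using a simple randomisation method". No blocking, stratification or minimisation is mentioned in either document.

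Section 4: "A total of 72 eligible subjects are planned to be randomised". Section 10.1 finds 80% power "when the sample size in each of the 4 groups is 16", then: "To allow for up to 10% drop-out, the sample size per group will be 18". Withdrawn participants are not replaced, and "it is expected that there will be at least 16 per group after withdrawals".

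Section 10.3.2 of the protocol and SAP tests TNF-α at 2 hours in the no-ticagrelor condition "by one-way ANOVA with treatment as a factor". The interim primary analysis (section 10.6) has the same form, on visits "anticipated to be split into approximately equal numbers receiving each of the eight study treatment regimens". The comparisons of each aspirin regimen with and without ticagrelor (section 10.3.3) are paired t-tests. Treatment period appears as a fixed effect only in the section 10.6 mixed models, which are used if the trial stops early.

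**The concern.** Simple randomisation fixes the total but not the group sizes. The sample-size section treats 18 and 16 per group as quantities the design will deliver, whereas under this scheme 18 is only the mean of a random count.

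The same applies to order. The no-ticagrelor visit that supplies the primary endpoint is the first endotoxin challenge in four sequences and the second in the other four. If responses differ between first and second challenge, that difference adds noise to the dose comparison. In any one trial with unequal order splits, it also shifts the dose and ticagrelor contrasts. A period term would remove it, and the plan uses one elsewhere but not in the analyses that decide the trial.

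**Working it through.** **The plan's own figure.** On the natural-log scale, increases of 0, 20, 40 and 60% give means 0, 0.182, 0.336 and 0.470. Their variance is V = 0.0307, and V/s² = 0.0307/0.410² = 0.1828, as printed. The noncentral F test with λ = 4n × 0.1828 on 3 and 4n − 4 degrees of freedom at α = 0.05 gives 80.2% at n = 16 and 77.1% at n = 15. Then 16/0.9 = 17.8, rounded up to 18, and 4 × 18 = 72. The calculation reproduces for equal groups.

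**Group sizes under simple randomisation.** Each aspirin group is Binomial(72, 1/4), with mean 18 and SD √(72 × 0.25 × 0.75) = 3.67. Exact multinomial and simulation (400,000 draws) results:

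- a given group has fewer than 16: 25%;
- all four have at least 16 at randomisation: 19.0%;
- smallest group: mean 13.7, and 13 or fewer in 41% of trials.

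**After drop-out, each participant retained with probability 0.9:**

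| | Simple | All 72 blocked |
|---|---|---|
| All four groups ≥ 16 | 1.8% | 29% |
| Mean power | 79.7% | 80.6% |
| 5th percentile of power | 71% | 76% |

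At 5% drop-out the first row becomes 7.4% v 79%.

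**Order split.** With 72 people over eight sequences, at least one dose group is split 2:1 or worse in 58% of trials. The mean absolute gap in the share having the no-ticagrelor visit first is 0.136 for a given pair of dose groups, and 0.25 between the highest and lowest of the four.

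**Size of a period effect on the dose comparison.** The documents give no period effect, so these sizes are assumptions. For a 20% lower response at the second challenge, |ln 0.8| = 0.223. A given pair shifts on average by 0.136 × 0.223 = 0.030, about 3%. The most divergent pair shifts by 0.25 × 0.223 = 0.056, about 5–6%.

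Simulated power with 64 completers (4,000 trials per scenario):

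| Assumed period effect (log scale) | Allocation | No period term | Period term |
|---|---|---|---|
| 0.20 | simple | 75% | 78% |
| 0.20 | blocked | 78% | 81% |
| 0.41 (1 SD) | simple | 70% | 79% |
| 0.41 (1 SD) | blocked | 68% | 80% |

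Under simple randomisation the unadjusted type I error stays at about 5% (5.1% and 4.8%). The adjustment recovers power that blocking alone does not.

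**Paired contrast.** With n₁ and n₂ participants in the two orders, the mean paired difference carries a period bias of |n₂ − n₁|/(n₁ + n₂) times the period effect. For 6:12 this is 6/18, one third. For 5:13 it is 8/18 = 0.44.

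**What blocking could still achieve.** Section 10.6 expects 46 participants past visit 3, leaving at most 72 − 46 = 26 allocations. With 46 simple and 26 blocked, and 10% drop-out, all four groups reach 16 in about 3.1% of trials, mean power is 80.0%, and the 5th percentile is about 72%.

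**The case against.** The strongest reply is that little is lost. Mean power falls by about 1 point. Section 10.1 speaks of an expectation and of drop-out up to 10%, and 18 × 0.9 = 16.2 completers is indeed the average. Even full blocking misses 16 in some group in 71% of trials, so much of the shortfall comes from the thin margin between 18 and 16. Simple randomisation is also a defensible choice in an open-label, single-centre trial whose investigators see every allocation, because the next one cannot be guessed. All of this stands.

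On period, section 7.7 sets a washout of at least 5 weeks and states that endotoxin tolerance is absent by then. That answers the most obvious mechanism. It does not exclude every difference between first and second challenge, and the early-termination models include period despite the washout.

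A reader might infer that the trial is seriously underpowered, that its type I error is inflated, or that the dose comparison is biased by design. The documents do not support these readings. Order is itself randomised, so the comparison is unbiased over allocations, and the shift arises only conditional on an uneven split. Nor should the 0.25 gap be read as typical, since it is the range across four groups. Nor would switching to blocks now obtain the 29% and 76%, which require all 72 to have been blocked from the start.

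**Conclusion.** The point holds as a modest one. The allocation method does not secure 18 randomised and at least 16 evaluable in every group: the chance is 19% for 16 at randomisation and 1.8% after 10% drop-out. The cost is about 1 point of mean power, with an unlucky tail near 71%, and no inflation of type I error.

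The more useful finding is the missing period term in the primary and interim ANOVAs and the paired t-tests. Under an assumed 20% period effect it would move a given between-dose difference by about 3%. A 6:12 order split would bias a paired ticagrelor contrast by one third of whatever period effect exists. These figures assume drop-out at random and equal allocation probabilities. The power figures also use the plan's effect sizes and SD. The documents neither estimate nor rule out a period effect.

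**What to change.** 1. Add period (first or second challenge) as a fixed effect in the primary and interim models for TNF-α at 2 hours. Cost: one residual degree of freedom (60 to 59 with 64 completers).
2. Replace the paired t-tests with a within-participant model containing ticagrelor and period. The SAP already specifies mixed models of this kind for early termination, so the extra work is small, again at one degree of freedom.
3. In section 10.1, restate 18 and 16 per group as expected values, and report power for the group sizes actually realised. No cost.
4. Optional: permuted blocks in multiples of 8, of varied size because the trial is open-label, for any allocations still to be made. This is a setting in the randomisation service with some loss of unpredictability. With 46 participants already past visit 3, it raises the chance of 16 in every group only from 1.8% to about 3%, and the 5th percentile of power from 71% to about 72%.
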